** Primary prevention defined as prevention of the first VTE event after the index surgery:

Table 4 Preliminary list of diagnoses and corresponding ICD-10-CM codes to identify on-label and off-label use for stroke prevention in non-valvular atrial fibrillation with dabigatran etexilate

Disease/condition or procedure	ICD-10-CM description	ICD-10-CM code	Use of codes in indication definitions
Atrial fibrillation	Atrial fibrillation and flutter	I48*	Primary code for the broad definition of the clinical indication
Valvular heart disease	Non-rheumatic mitral valve, aortic valve, tricuspid valve, pulmonary valve disorders Endocarditis, valve unspecified Endocarditis and heart valve disorders in diseases classified elsewhere	I34*- I39*	Sub-group of exclusive codes for the restrictive definition within the clinical indication
	Chronic rheumatic heart diseases	I05*-I08*, I09.1	Sub-group of exclusive codes for the restrictive definition within the clinical indication
	Congenital malformations of pulmonary and tricuspid valves Congenital malformations of aortic and mitral valves	Q22*-Q23*	Sub-group of exclusive codes for the restrictive definition within the clinical indication
	Presence of heart valve replacement Presence of xenogenic heart valve	Z95.2* - Z95.4*	Sub-group of exclusive codes for the restrictive definition within the clinical indication

Table 4 (cont'd) Preliminary list of diagnoses and corresponding ICD-10-CM codes to identify on-label and off-label use for stroke prevention in non-valvular atrial fibrillation with dabigatran etexilate

Disease/condition or procedure	ICD-10-CM description	ICD-10-CM code	Use of codes in indication definitions
	Mechanical complication of heart valve prosthesis Mechanical complication of coronary artery bypass graft and biological heart valve graft Infection and inflammatory reaction due to cardiac valve prosthesis	T82.0* T82.2* T82.6*	Sub-group of exclusive codes for the restrictive definition within the clinical indication
Stroke, transient cerebral ischaemia (TIA)	Cerebral infarction; occlusion and stenosis of pre-cerebral or cerebral arteries; TIA; acute, but ill-defined, cerebrovascular disease; sequelae of cerebral infarction	I63*-I66* I69.3* G45	Secondary code to support clinical indication
Symptomatic heart failure	Heart failure	I50*	Secondary code to support clinical indication
Systemic embolism	Arterial embolism and thrombosis	I74*	Secondary code to support clinical indication

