Diabetes	Diabetes mellitus	E10*-E11*	Secondary code to support clinical indication
Hypertension	Hypertensive disease	I10*-I15*	Secondary code to support clinical indication
Coronary heart disease	Ischaemic heart disease	I20*-I25*	Secondary code to support clinical indication

* = wild card character indicating additional subcodes under this primary code; ICD-10-CM = International Statistical Classification of Diseases and Related Health Problems, 10th Revision, Clinical Modification 2014 version. Procedural codes will be refined based on the dictionary system in place in each database

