Anticoagulation for patients with heart valve replacement or a stent	Heart valve replacement Insertion of coronary stent, bypass anastomosis for heart revascularisation	See codes in Table 4 Z95.1 Z95.5	For stent or aorto-coronary bypass surgery in absence of atrial fibrillation (see Table 4)
General prophylaxis or treatment of a thrombus in any site	Malignancies	C00-C97	In absence of codes in Table 3 or Table 4
Patients with hypercoagulability	Antiphospholipid syndrome	D68.61	In absence of codes in Table 3 or Table 4

* = wild card character indicating additional subcodes under this primary code; ICD-10-CM = International Statistical Classification of Diseases and Related Health Problems, 10th Revision, Clinical Modification, 2014 version. Procedural codes will be refined based on the dictionary system in place in each database

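### Table 5 withholds off-label status in the malignancy and antiphospholipid rows from users with any Table 4 code, including hypertension or diabetes, so off-label use can be understated

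*Protocol*

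**What the plan says.** Section 3.5.1 sets two levels of on-label use. The broad level rests on the main code of an approved indication. The restrictive level then removes patients for whom the drug might not be indicated, for example those with valvular disease.

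The tables give each code a role:

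- Table 4 marks one row, "Atrial fibrillation and flutter" (I48*), as "Primary code for the broad definition of the clinical indication". Table 3 gives the same role to artificial hip (Z96.64*) and knee (Z96.65*) joints.
- Table 4 also lists stroke/TIA, heart failure, systemic embolism, "Diabetes mellitus", "Hypertensive disease" and "Ischaemic heart disease", each as "Secondary code to support clinical indication". It further lists valve codes that serve only as exclusions at the restrictive level.
- Table 3 also lists venous thromboembolism (VTE) codes, again as exclusions.

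Section 3.5.2 defines off-label use as use for a condition other than the labelled indications and patient sub-groups. It gives an open-ended list of examples that apply when no labelled indication is present. Table 5 turns these into codes. Its malignancy and antiphospholipid rows apply "In absence of codes in Table 3 or Table 4". Its neighbours are narrower: the injury and fracture row requires only that hip or knee surgery codes be absent, and the stent and bypass row is limited to absence of atrial fibrillation ("For stent or aorto-coronary bypass surgery in absence of atrial fibrillation (see Table 4"). The VTE row carries no condition.

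**The concern.** The condition on the two rows covers every code in Tables 3 and 4, but only three entries there (I48*, Z96.64*, Z96.65*) establish a labelled indication. The rest are comorbidities that support an atrial fibrillation indication already present, or exclusions from one. A hypertension code says nothing about why an antiphospholipid patient received dabigatran, yet it switches the off-label row off without switching any on-label definition on.

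The off-label proportion is the main outcome (Section 3.5), in a study that the regulator requested to assess off-label use. Through this rule the error can run only towards a lower proportion. It would also depend on how fully comorbidity is recorded, which differs by source: Table 1 shows no hospital diagnoses in Cegedim, while Denmark has hospital diagnoses, with primary care diagnoses in DAMD. Any loss could therefore differ by country and carry into the pooled estimate of Section 3.7.1.

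**Working it through.** **Table 2 first.** The exact (Clopper-Pearson) binomial interval for 250 of 5,000 is 4.412% to 5.641%, which rounds to the printed 4.4-5.6. All 20 intervals in Table 2 reproduce this way. The half-width at 5% is (5.641 - 4.412)/2 = 0.61 points, and at 10% it is (10.865 - 9.182)/2 = 0.84 points.

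**The rule applied to three users**, none with I48*, Z96.64* or Z96.65*:

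| User | Broad on-label? | Malignancy or antiphospholipid row? | Other Table 5 row? | Result |
|---|---|---|---|---|
| D68.61 only | No | Yes | No | Off-label |
| D68.61 + I10 | No | No, I10 is in Table 4 | No | Neither group |
| C00-C97 + I10 + I26* | No | No | Yes, VTE | Off-label, as VTE only |

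The first two users differ only in hypertension, which is not an indication for the drug. Under the Section 3.5.2 definition both lack a labelled indication.

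**Who is lost from the total.** Only users whose sole Table 5 match would be one of the two rows. The VTE codes in Table 3 (I80.1*, I80.2*, I82.3*, I26*) are the same codes as in Table 5's VTE row, so users barred by those codes are still caught there while VTE use counts as off-label. Users with a valve replacement code, or with a stent or bypass code and no atrial fibrillation, are caught by the valve and stent row.

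**Illustration of size.** Let m be the share of all users who would match only these two rows, and q the chance that such a user carries a Table 4 code other than I48*. Loss in percentage points = 100 × m × q. The protocol gives neither m nor q; both are assumptions.

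- m = 2% is 100 of 5,000 users.
- q = 40%: 100 × 0.4 = 40 lost, and 40/5,000 = 0.8 points.
- q = 70%: 100 × 0.7 = 70 lost, and 70/5,000 = 1.4 points.
- A loss equal to the 0.6-point half-width needs 0.006 × 5,000 = 30 users.

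For a wider range, write the recorded proportion as P × (1 - s × q), where P is the true off-label proportion and s the share of off-label users who match only these rows (so m = P × s).

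- P = 5%, s = 10%, q = 50%: 5 × (1 - 0.05) = 4.75%, a loss of 0.25 points.
- P = 5%, s = 50%, q = 90%: 5 × (1 - 0.45) = 2.75%, a loss of 2.25 points.
- P = 10%, same two settings: 9.5% and 5.5%.

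The low end lies inside the sampling error of Table 2; the high end is well outside it.

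**Shares by indication.** Take 250 off-label users, of whom 100 (40%) match only these rows. If the affected users vanish, the rows' share becomes 60/210 = 28.6% at q = 40%, or 30/180 = 16.7% at q = 70%. If a residual rule keeps them as off-label without an assigned indication, it becomes 60/250 = 24% or 30/250 = 12%. It falls either way.

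**The case against.** The strongest reply is that Table 5 is not the governing rule. It is labelled preliminary, Section 3.5.2 leaves the final list and algorithms to the database-specific protocols, and the definition in the text is broad and open-ended. The condition could be meant as shorthand for absence of the indications that Tables 3 and 4 define. Section 3.3.5.1 also plans a profile review in CPRD that may lead to modified algorithms. Part of this stands: the text definition is sound and the error is easy to repair. But Section 3 makes the common protocol the basis of every database protocol, and adjacent rows of the same table name the narrower condition. Three teams could copy the wording or repair it in three different ways.

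A second reply is that Appendix 4, which classifies on- and off-label use in a diagram, may assign unmatched users. That is possible. A residual rule there would protect the total, but not the shares by indication.

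Three stronger readings are tempting and not supported:

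- *That 0.8-1.4 points are lost.* The inputs are assumed, and users also caught by the VTE row or the valve and stent row are not lost.
- *That every affected user is truly off-label.* A malignancy code is a comorbidity, not a recorded reason for treatment. Section 3.3.5 expects some users without a clear indication, and a patient with cancer, heart failure and prior stroke may have unrecorded atrial fibrillation.
- *That the valve row wrongly classifies atrial fibrillation patients twice.* It does lack an atrial fibrillation exemption for valve replacement. But Section 3.5.1 brings contraindications into the on-label definition, prosthetic valves requiring anticoagulation are a listed contraindication since January 2013 (Section 1), and Section 3.7.1 includes contraindications in the main analysis. What is missing is only a statement of which level the row serves.

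**Conclusion.** The point holds as a defect in the wording of two Table 5 rows. Read literally, they conflict with the off-label definition in Section 3.5.2 and leave some users in neither group. The overall off-label proportion is understated unless another row or Appendix 4 captures those users; the shares of these two indications, where reported, are understated regardless. The direction follows from the text. The size does not: the illustrated 0.8-1.4 points rest on m = 2% and q = 40-70%, and plausible inputs also give a loss below the sampling error. The wording should be corrected before the database-specific algorithms are fixed.

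**What to change.** In the malignancy and antiphospholipid rows of Table 5, replace the condition with: *in absence of the primary codes (I48\*; Z96.64\*, Z96.65\* or the matching procedure codes)*. Carry this into each database-specific algorithm.

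Add one sentence to Section 3.5.2 stating that users with no labelled indication and no Table 5 match are reported as a separate group, unless Appendix 4 already assigns them.

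For the valve replacement row, state whether it applies at the broad or the restrictive level, consistently with Sections 3.5.1 and 3.7.1. The other rows need no new condition for this purpose.

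The cost is two table cells, a sentence or two of text and the matching algorithm code. No new data are needed.

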[Table 3](#) and [Table 4](#) display the preliminary lists of diseases, conditions, and procedures mapped to the ICD-10-CM codes for identification of the current approved indications. ICD-10-CM codes are used in the Danish national databases and in Cegedim (France); Read codes and ICD-10-CM codes are used in the CPRD (UK). These lists of codes will be used to identify the group of on-label users of dabigatran etexilate in each population. The complete list of codes will be available in the detailed, database-specific study protocol.

Two levels of on-label use will be investigated:

- The first level will include a broad definition based on the main code(s) for the approved clinical indications, e.g., atrial fibrillation.
- The second level will include a more restrictive definition by excluding patients with conditions for which the medication might not be indicated within the broad definition, e.g., valvular heart disease or low-risk patients with non-valvular atrial fibrillation.

Table 3 Preliminary list of diagnoses and corresponding ICD-10-CM codes for identification of new users of dabigatran etexilate for primary prevention of venous thromboembolism following total hip or knee replacement surgery

Disease/condition or procedure	ICD-10-CM description	ICD-10-CM code	Use of codes in indication definitions
Total hip replacement	Presence of artificial hip joint	Z96.64*	Primary code for the broad definition of the clinical indication
Total knee replacement	Presence of artificial knee joint	Z96.65*	Primary code for the broad definition of the clinical indication
Absence of venous thromboembolism between total hip or knee replacement surgery and dabigatran etexilate initiation **	Phlebitis and thrombophlebitis of femoral vein Phlebitis and thrombophlebitis of other and unspecified deep vessels of lower extremities Acute embolism and thrombosis of deep veins of lower extremity Pulmonary embolism	I80.1*; I80.2*; I82.3*; I26*	Sub-group of codes for exclusion of VTE in the restrictive definition within the clinical indication

* = wild card character indicating additional subcodes under this primary code; ICD-10-CM = International Statistical Classification of Diseases and Related Health Problems, 10th Revision, Clinical Modification, 2014 version. VTE = venous thromboembolism. Procedural codes will be included based on the dictionary system in place in each database.

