3.5.2 Off-label use definition

The definition of off-label use of oral dabigatran etexilate outside AF will be based on the use for a disease or medical condition other than the labelled indications and patient sub-groups given in Section [3.5.1](#). The dabigatran indications approved at the time of the index date will be used to define off-label use for each new user identified in the study period. In the absence of labelled indications, potential off-label use could include, but is not limited to, the following:

- General thrombosis prophylaxis other than hip and knee orthopaedic surgery.
- Treatment of deep vein thrombosis (DVT) and pulmonary embolism (PE) and prevention of recurrent DVT and PE in adults (CHMP opinion 25 April 2014), until Commission Decision
- Anticoagulation for patients with heart valve replacement or a stent.
- General prophylaxis or treatment of a thrombus in any site.
- Patients with hypercoagulability (e.g., factor V Leiden thrombophilia).

A preliminary list of ICD-10-CM codes to identify these conditions is provided in [Table 5](#). The final list will be included in the detailed, database-specific study protocol. In addition, the set of algorithms to be used as proxies for identification of potential clinical indications will be defined and described in the detailed, database-specific study protocol. These proxies will be based on codes for the presence of certain diseases and clinical conditions and the use of certain medications (e.g., use of other oral anticoagulants).

Because dabigatran etexilate has been approved for use only in adults, any identified use in the pediatric groups of age will be considered off-label. New users of dabigatran etexilate aged younger than 18 years at the index date will be considered in the pediatric population.

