The proportion of users with each of the contraindications, including those based on comedication, disease, or severity of conditions, such as patients with severe renal impairment, will be also described. In those databases with laboratory test results available, severe renal impairment will be defined as creatinine clearance < 30 mL/min from directly recorded information of the estimated renal function, as available. For those patients with serum creatinine levels and patient weight available, we might estimate glomerular filtration rate by using the Cockcroft-Gault equation and/or the CKD-EPI equation [[R13-5416](#)]. However, it is important to be aware that actual values of laboratory test results will be inconsistently recorded in most databases and data will be limited. We will also capture those patients with ICD-10-CM codes for advanced renal disease—N18.4-N18.6, chronic kidney disease, stages 4 and 5 (severe), and end-stage renal disease—as available in each database according to the coding system and version in place.

Given the different recommended dosage regimens in both the approved and the new indications, new users of dabigatran etexilate will be described according to dose categories, but dose will not be included in the study definition of off-label use based on the first level of on-label indications.

Dose will be incorporated in the definition of off-label use based on the second level, which is a more restrictive definition of on-label use (see [Appendix 4](#)). In addition, the proportion of new users within the primary VTE prevention subgroup with one or more follow-up prescriptions after the recommended treatment duration will be described. The follow-up prescriptions will be assessed in the 90-day time window after the index prescription..

Table 5 Preliminary list of diagnoses and corresponding ICD-10-CM codes for identification of potential off-label clinical indications of dabigatran etexilate

Disease/condition or procedure	ICD-10-CM description	ICD-10-CM code	Use of codes in off-label indication definitions
Treatment or secondary prevention of venous thromboembolism	Venous thrombosis Pulmonary embolism	I80.1*, I80.2*, I82.3* I26*	
General thrombosis prophylaxis other than hip and knee orthopaedic surgery	Injuries to the knee and lower leg Fracture of femur	S80*-S89* S72*	In the absence of codes for hip or knee orthopaedic surgery (see Table 3)

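### In Table 5, the malignancy and antiphospholipid rows are blocked by any code in Tables 3 or 4, including risk-factor and exclusion codes that are not labelled indications

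*Protocol*

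**What the plan says.** Section 3.5.2 of the Protocol defines off-label use as "based on the use for a disease or medical condition other than the labelled indications and patient sub-groups given in Section" 3.5.1. Table 5 then gives preliminary code lists for potential off-label indications, some with a condition attached:

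- Malignancy and antiphospholipid syndrome: "In absence of codes in Table 3 or Table 4".
- Knee and lower-leg injury or femur fracture: "In the absence of codes for hip or knee orthopaedic surgery (see Table 3").
- Stent or bypass: "For stent or aorto-coronary bypass surgery in absence of atrial fibrillation (see Table 4").
- VTE: no condition.

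Tables 3 and 4 in Section 3.5.1 contain three kinds of code:

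- The codes that establish a labelled indication are Z96.64* and Z96.65* in Table 3 and I48* in Table 4. Each is marked "Primary code for the broad definition of the clinical indication".
- Stroke/TIA, heart failure, systemic embolism, diabetes, hypertension and coronary heart disease in Table 4 are each marked "Secondary code to support clinical indication".
- Exclusion codes are the valve codes in Table 4 ("Sub-group of exclusive codes for the restrictive definition within the clinical indication") and the VTE codes in Table 3 ("Sub-group of codes for exclusion of VTE in the restrictive definition within the clinical indication").

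**The concern.** The condition on the two rows does not separate codes that establish a labelled indication from codes that only support or exclude one. A risk-factor code has meaning for the label only alongside atrial fibrillation. Without I48* it does not make the use on-label, yet under the Table 5 wording it is enough to stop a cancer or antiphospholipid user from being counted. Valve codes, which take patients out of restrictive on-label use, have the same blocking effect.

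Section 3.7.1 plans, as part of the main analysis, to describe the share of each of the most common off-label indications, so an undercount in these rows goes straight into a reported result. The loss may also differ by country, because Table 1 shows that diagnosis capture differs: Cegedim has no hospital diagnoses, and in Denmark primary care diagnoses come only from the general practice database. In Denmark the indication rests on proxies, so the coding rule carries more weight there.

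**Working it through.** **1. Trace one user through the rules.** Take a user with a malignancy code and a hypertension code (I10*-I15*), without I48*, Z96.64* or Z96.65*.

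- Broad on-label definition: not met, because no primary code is present.
- General off-label definition in Section 3.5.2: met in substance, because no labelled indication is recorded.
- Malignancy row of Table 5: not met, because hypertension is a Table 4 code.
- Other rows of Table 5: not met unless the user also has a VTE, injury or fracture, valve-replacement, stent or bypass code.

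The same happens to a user with antiphospholipid syndrome and a past stroke.

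**2. Compare the conditions within Table 5.** The fracture row asks only about hip or knee surgery. The stent/bypass row asks only about atrial fibrillation. Both test for the labelled indication itself. The malignancy and antiphospholipid rows test for any code in either table.

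**3. Reproduce the protocol's precision figures.** Table 2, n = 5,000, exact (Clopper-Pearson) 95% limits:

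- 2% (100 users): 1.63-2.43; Table 2 prints 1.6-2.4.
- 5% (250 users): 4.41-5.64; Table 2 prints 4.4-5.6.

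All 40 limits in Table 2 agree with this method after rounding.

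**4. Illustrate the loss from the two rows.** Let t be the true share of users belonging in these rows and q the share of them with a blocking code but no primary code. The row share counted is t × (1 − q). The documents give neither t nor q; t = 2% and the values of q are assumptions. With n = 5,000, the true count is 5,000 × 0.02 = 100.

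| q (assumed) | Counted | Row share | Exact 95% CI |
|---|---|---|---|
| 20% | 80 | 1.6% | 1.27-1.99 |
| 40% | 60 | 1.2% | 0.92-1.54 |
| 50% | 50 | 1.0% | 0.74-1.32 |
| 60% | 40 | 0.8% | 0.57-1.09 |
| 80% | 20 | 0.4% | 0.24-0.62 |

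At q = 20% the upper limit is already just below the true 2%.

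**5. See whether q can be bounded.** Assume five Table 4 conditions occur independently. Then q = 1 − the product of (1 − prevalence). With assumed prevalences of 20, 5, 5, 3 and 3%, q = 1 − 0.80 × 0.95 × 0.95 × 0.97 × 0.97 = 32%. With 60, 20, 25, 10 and 15%, q = 1 − 0.40 × 0.80 × 0.75 × 0.90 × 0.85 = 82%. The range lies on both sides of one half, so the documents cannot say whether the loss is a minority or a majority.

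**6. Effect on the total, under a condition.** Suppose the numerator is the union of the Table 5 rows and no blocked user fits another row. With an assumed true total of 5%, the reported total is 5% − 2% × q: 4.6% at q = 20%, 4.4% at 30%, 4.0% at 50% and 3.4% at 80%. At 20% this is still inside Table 2's 4.4-5.6; at 30% it is at the lower limit. If blocked users are counted as off-label by the general definition, the total does not change.

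**The case against.** The strongest reply is that the condition is shorthand. Section 3.5.2 introduces its list as applying where labelled indications are absent, and Section 3.5.1 says Tables 3 and 4 serve to identify on-label users. On that reading the two rows simply mean that no on-label indication is present. In addition, Table 5 is preliminary, final lists and algorithms are left to the database-specific protocols, and at least 200 CPRD profiles will be reviewed to validate the algorithms.

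That reading may be what was meant, but it is not what the rows say, and neighbouring rows in the same table state the narrower condition outright. The database-specific protocols are built on this common document, so the wording is likely to be carried over unless corrected. The profile review is planned only in CPRD and would not show the effect in Denmark or France.

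Two stronger inferences are tempting, and the documents do not support either. The first is that most true off-label users in these rows are lost: no figure for the share is given, and plausible assumptions fall on both sides of half. The second is that these users certainly drop out of the main numerator. The Section 3.5.2 list is expressly open-ended, such users also fail the broad on-label definition, and no visible text makes the numerator the sum of the Table 5 rows. Appendix 4, which holds the diagram of on-label and off-label categories, is not in the text at hand and may settle their class. Users with VTE, fracture, valve-replacement, stent or bypass codes can also be counted in other rows.

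**Conclusion.** The condition on the malignancy and antiphospholipid rows is wrong as written. It lets secondary and exclusion codes block users who have no labelled indication, against the definition in Section 3.5.2 and unlike the fracture and stent/bypass rows. The consequence that follows from the text alone is an undercount in these two rows of the planned breakdown, by a share that the documents do not give. The 1.6% in place of 2% is an illustration that rests on the assumed 2% share and 20% loss. A downward bias in the overall off-label proportion is conditional: it arises only if the numerator is built from the Table 5 rows and the blocked users fit no other row.

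**What to change.** In both rows of Table 5, make the condition the absence of the primary codes only: Z96.64* and Z96.65* with the corresponding database-specific replacement procedure codes (Table 3), and I48* (Table 4). In addition:

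- State that secondary and exclusion codes never block an off-label row.
- State how users with neither a labelled indication nor a Table 5 row are handled: either counted as off-label under an other category, or reported as a separate unclassified group. Align this with Appendix 4.
- Either set a full order of precedence across all Table 5 rows, or let a user appear in several rows while counting once in the total. Precedence for VTE alone is not enough: a user with a valve replacement and cancer would still fall in two rows.

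The cost is a few lines in Section 3.5.2 and Table 5, carried into the database-specific algorithms. No new data are needed. The change should be made before the database-specific protocols are finalised.
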